14.7 Efficacy Analysis

14.7.1 Primary Efficacy Analysis

The repeat opioid OD or opioid-related death primary endpoint analysis will be performed using Cox proportional regression and compare the SUBLOCADE treatment arm to historical and concurrent control data. Propensity scores will be used to match study participants to controls. Repeat OD and deaths (measured as time-to-event or censored at 6 months post index OD) will be tracked using subject reports, electronic medical records and state death registries. Events will be counted within the 6 months of treatment period for all treated subjects.

Propensity score analysis will be used in the analysis of SUBLOCADE vs. the control for time to repeat OD or opioid-related death. Study subjects will receive a propensity score that will be matched to propensity scores in the control data. The propensity score, p , will also be used as a weight in the Cox proportional hazards model. All SUBLOCADE treatment group subjects will have a weight of $p=1$ and patients in the control groups will be weighted by $p/(1-p)$. Here p can be viewed as the probability that the control subject would have been a study participant if the study were performed during their treatment.

The propensity score will be estimated by fitting a logistic regression on a dataset consisting of the consenting subjects (subjects in the SUBLOCADE arm at VCU) and the controls. The response variable will be consent to treatment; predictors will include baseline characteristics such as subject age, gender, county, race and insurance status. This model will be used to generate the predicted probability of consent to participate among the controls.

The Cox proportional hazards model will use the controls as the reference group and code the SUBLOCADE arm as a factor variable. The analysis will test the coefficient for the SUBLOCADE arm versus the controls from the Cox regression, with the interpretation of the exponential (coefficient) as the hazard ratio for time to repeat OD or opioid-related death in subjects consenting to the active treatment group versus the control cohorts.

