The probabilities for the control cohort will be used as weights in the Cox proportional hazards model. The weights serve to make the control cohort appear similar to the treatment group on the observed baseline characteristics; this will be checked using covariate balance diagnostics. The weights will provide greater weight for control patients who likely would have participated if offered a prospective trial of SUBLOCADE and lesser weight for patients unlikely to have consented.

In addition, the results will be illustrated with a Kaplan-Meier curve.

The analysis will take place once all subjects have completed the trial and sufficient time has passed to allow the state death registries to be updated.

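### Section 14.7.1 describes the control weight in two ways, as the odds p/(1-p) and as the probability p; only the odds achieve the balance that the section aims for

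*Combined protocol and SAP*

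**What the plan says.** All the relevant text is in section 14.7.1 (Primary Efficacy Analysis) of the combined protocol and SAP.

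- **Second paragraph, lead-in:** "The propensity score, p , will also be used as a weight in the Cox proportional hazards model".
- **Second paragraph, formula:** "All SUBLOCADE treatment group subjects will have a weight of" 1 (printed there as p=1), while "patients in the control groups will be weighted by" p/(1-p).
- **Third paragraph:** p comes from a logistic regression of consent on characteristics such as age, gender, county, race and insurance. "This model will be used to generate the predicted probability of consent to participate among the controls".
- **Fifth paragraph:** "The probabilities for the control cohort will be used as weights in the Cox proportional hazards model". The purpose follows: "The weights serve to make the control cohort appear similar to the treatment group on the observed baseline characteristics". Balance is to be checked with diagnostics, for which no threshold or follow-up action is given.

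The first and second paragraphs also say that participants will be matched to controls on the propensity score.

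Nothing elsewhere settles which weight governs. Table 2 names only propensity scores within a Cox regression. The statistical methods in the synopsis describe a Cox model controlling for route of administration and comorbid substance use disorder, and do not mention weights.

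**The concern.** The study is open-label and has no randomised control, so this weighting is central to the confounding adjustment of the primary comparison. The lead-in to the formula and the opening of the fifth paragraph both name p as the weight; the formula between them names the odds. A programmer working from the fifth paragraph would fit a different estimator from one working from the second. The two can give different primary hazard ratios, and the text leaves the choice open until after outcomes are known.

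**Working it through.** **Plan's own figures.** No figure in the documents depends on the control weight. The nearest, 80% power for 99 versus 198 at 3% versus 11.5% (section 14.2), reproduces at 80.3% with a one-sided 5% Fisher exact test, but involves no weighting. Only the group sizes are used below.

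**Algebra.** Let f(x) be the covariate distribution in the combined dataset and p = p(x).

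- Treated subjects: density proportional to f·p.
- Controls: density proportional to f·(1-p).
- Controls weighted by p/(1-p): f·(1-p)·p/(1-p) = f·p, the treated mix.
- Controls weighted by p: f·p·(1-p), an overlap mix. This differs from the mix of treated subjects held at weight 1, unless p is constant.

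**Worked example.** Assumption: one binary factor X, present in 60% of treated subjects and 30% of controls. Sizes: 99 and 198.

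| | X=1 | X=0 |
|---|---|---|
| Treated | 59.4 | 39.6 |
| Controls | 59.4 | 138.6 |
| p | 59.4/118.8 = 0.500 | 39.6/178.2 = 0.222 |
| Controls × p | 29.7 | 30.8 |
| Controls × p/(1-p) | 59.4 | 39.6 |

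- Prevalence in controls under p: 29.7/(29.7+30.8) = 49.1%. Share of the imbalance left: (60-49.1)/(60-30) = 36%.
- Prevalence in controls under p/(1-p): 59.4/(59.4+39.6) = 60%. Nothing is left.
- Same prevalences at 1:5: 54.4% under p, 19% left. At 1:10: 56.9%, 10% left.

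**Effect on the hazard ratio.** Take no drug effect and let X multiply the hazard by k. The apparent hazard ratio under p is approximately (1+(k-1)×0.6)/(1+(k-1)×0.491).

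- k=2: 1.6/1.491 = 1.07. k=3: 2.2/1.982 = 1.11.
- Prevalences reversed (30% treated, 60% controls): p is 0.2 and 0.467, and prevalence under p is 23.76/(23.76+36.96) = 39.1%. This gives 1.3/1.391 = 0.93 for k=2 and 1.6/1.783 = 0.90 for k=3.

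**Continuous covariate.** A large-sample simulation used 2,000,000 subjects, one standard normal covariate, log-odds of consent of 0.5 or 1.0 per SD, log-hazard of -0.5, 0 or +0.5 per SD, and a control risk of about 11.5%. All these values are assumptions apart from the 11.5%. At 1:2:

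- Standardised mean difference: 0.49 to 0.91 unweighted, 0.17 to 0.34 under p, about 0 under p/(1-p).
- Hazard ratio when the truth is 1 and the covariate is prognostic: 0.87 to 1.18 under p, within about 1% of 1 under p/(1-p).
- If the covariate is not prognostic, p causes no bias.
- At 1:19 under p: standardised mean difference 0.03 to 0.09, hazard ratio about 0.94 to 1.05.

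**Interaction with matching.** Suppose the odds weights come from the full pool but are applied to controls already matched to 60% prevalence. The weights are 1 for X=1 and 39.6/138.6 = 0.286 for X=0, a ratio of 3.5. Prevalence becomes 0.6×3.5/(0.6×3.5+0.4) = 84%, an overshoot. The formula therefore balances only when applied to the unmatched set that produced p.

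**The case against.** The strongest reply is that only one formula is written, p/(1-p), and it directly follows the sentence calling p a weight. The authors use p loosely: the treated weight is printed as p=1, which is not a fitted propensity score. The fifth paragraph may be the same shorthand in a plain-language recap. This stands. A reader might infer that the plan commits to weighting by p and that the primary hazard ratio will be biased; the documents support neither.

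A reader might also infer that p leaves controls unlike the treated group. It does not: at 1:2 it removes roughly 64% of the imbalance, and more with a larger pool. The 99:198 ratio comes from the power section. Controls are drawn from overdose visits from 2015 onward, and the size of the propensity dataset is not stated.

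The possible bias is modest against the trial's precision. At the planned rates, expected events are about 3 (99×0.03) and 23 (198×0.115), so SE(log HR) is about √(1/3+1/23) = 0.61. The example's bias of log 1.07 to log 1.11, or 0.07 to 0.10, is under one fifth of that. Nothing in the documents shows how prognostic the named predictors are.

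The balance diagnostics are a partial safeguard. They should reveal 49% against 60%, but with no threshold or action stated they need not force a correction.

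What survives is that the fifth-paragraph sentence, taken as written, does not deliver the aim stated straight after it, and no other text overrides it.

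**Conclusion.** Wrong as written, in the sense of an inconsistency in the primary estimator rather than a settled plan to weight by p. With treated weight 1, p/(1-p) meets the section's aim and p meets it only partly. In the 60% versus 30% example, p leaves about 36% of the imbalance at 1:2, 19% at 1:5 and 10% at 1:10. The hazard ratio under a true value of 1 could then read about 0.90 to 1.11 at 1:2. That bias requires both that p is used and that the predictors are prognostic; it can go either way and shrinks as the control pool grows. The prevalences, the hazard multipliers and the use of 1:2 for the propensity dataset are assumptions. Nor do the documents support inferring that p/(1-p) guarantees balance whatever else is done: that fails if the weights are laid over matched controls.

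**What to change.** In section 14.7.1:

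1. Replace the opening sentence of the fifth paragraph with a statement that each control is weighted by the odds p/(1-p).
2. In the second paragraph, replace the sentence calling p a weight with: *Weights derived from p will be used.*
3. State that these weights apply to the full unmatched control set from which p was estimated, and are not added on top of propensity matching. Reconcile the two matching statements with this.
4. Compute the balance diagnostics with the same weights, preferably with a stated threshold and the action to take if it is missed.

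The cost is a few sentences of text and no change to data collection. There is one small downside: odds weights can be more variable than p. They are, however, already the only formula the plan writes out.

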14.7.2 Secondary/Exploratory Endpoint Analysis

Treatment retention at 3 and 6 months will be analysed utilizing a logistic regression, comparing subjects who have primarily intravenous to non-intravenous opioid use as determined using the MINI.

The analysis of the exploratory endpoints (incidence rate of repeat OD, illicit opioid use as measured by UDS and opioid craving, as measured by the OC-VAS) is detailed in Table 2.

These analyses will be performed using the treatment population.

A summary of the primary, secondary, and exploratory endpoint analyses is shown in Table 2.

Table 2 Summary of Efficacy Analysis Strategy

Endpoint	Statistical Method	Analysis Population	Missing Data Approach	Analysis Timepoint
Primary Efficacy Endpoint:				
Repeat OD or Death	Propensity scores within Cox PH Regression	Treatment	No imputation	EOT (6 months)
Secondary Efficacy Endpoints:				
Treatment retention at 3 and 6 months	Logistic Regression	Treatment	No imputation	EOT (6 months)
Exploratory Endpoints:				
Illicit opioid use as measured by urine drug screen (UDS) results	Hierarchical generalized linear modeling (HGLM)	Treatment	Missing UDS during treatment will be imputed as non-negative for opioids. Missing UDS if lost to follow-up will be imputed as missing.	EOT (6 months)
Opioid craving in subjects as measured by Craving Visual Analog Scale (VAS) scores.	Logistic Regression, ANCOVA	Treatment	No imputation	EOT (6 months)
Genetic predictors of treatment response and repeat OD.	Logistic Regression, ANCOVA	Treatment ^a	No imputation	EOT (6 months)
Predictability of treatment response based on impulse control as measured by decision making in the delay discounting task.	Logistic Regression, ANCOVA	Treatment	No imputation	EOT (6 months)
Retention in treatment between ED initiated Suboxone/Sublocade compared to Outpatient initiated Suboxone/Sublocade	Cox PH Regression	Treatment	No imputation	EOT (6 months)

^a This analysis will only include subjects within the treatment population that consented to participate in the PGx sub-study.

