Once subjects are engaged in care at the treatment clinic, they will continue to receive SUBLOCADE for 6 months. The second 300 mg injection will be administered on Day 8 (-0/+4 days) after the first injection, with subsequent 300 mg injections administered at 28-day (-2/+4 days) intervals over approximately 6 months for a total of 7 injections. If necessary, for tolerability, the dose of SUBLOCADE can be reduced to 100 mg. All subjects will receive site standard psychosocial therapy at least weekly during the first 3 months of treatment, and twice monthly thereafter if clinically stable.

All subjects will complete an End of Treatment (EOT) / Early Termination (ET) visit 28 days after their last injection of SUBLOCADE. Within 3 months prior to or at the EOT visit, the Investigator or a medically qualified sub-investigator will discuss the subject's available treatment options and arrange referral. All subjects will receive a safety follow-up telephone call, 30 days after their EOT/ET visit to assess AEs, SAEs, pregnancy status (if applicable) and concomitant medications. Subjects who decline to continue in medication assisted treatment (MAT) will receive monthly safety follow-up phone calls for an additional 5 months (6 months total) to assess SAEs, pregnancy status (if applicable) and concomitant medications.

Primary Endpoint(s):

The primary endpoint of this study is:

- Time to repeat OD or opioid-related death. Repeat OD or opioid-related death will be measured from electronic medical records and state death registries.
- Additional comparisons on repeat OD and death rates will be made to concurrent patients who decline to participate in the SUBLOCADE injection.

Secondary Endpoint(s):

The key secondary endpoint of the study is:

- Treatment engagement as measured by attending the outpatient clinic and receiving subsequent buprenorphine treatment at 3 and 6 months.

The secondary endpoints of this study are:

- Numbers and percent of subjects in treatment at 3 and 6 months after opioid OD.

Exploratory Endpoints:

The exploratory endpoints of this study are:

- Opioid craving in subjects as measured by Craving Visual Analog Scale (VAS) scores.
- Illicit opioid use as measured by urine drug screen (UDS) results.
- Genetic predictors of treatment response and OD.

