- Predictability of treatment response based on impulse control as measured by decision making in the delay discounting task, and opioid cravings/valuation as measured by the brief opioid demand task.
- Healthcare resource utilisation as compared to the historical control (2015-2018) obtained from VCU anonymized health records.
- Treatment effectiveness as measured by Treatment Effectiveness Assessment (TEA), medication satisfaction as measured by the Medication Satisfaction Questionnaire (MSQ), and employment, presentism and absenteeism as assessed by the Work Productivity and Activity Impairment Questionnaire: Specific Health Problem (WPAI:SHP).

Safety Assessments:

Safety assessments include the proportion of subjects with AEs of the following types at any time during the treatment period: at least 1 AE, a drug-related AE, an SAE, a serious and drug-related AE, or an AE leading to treatment discontinuation.

Additional safety assessments include laboratory assessments, brief physical examinations, vital signs and concomitant medications. Worsening or initiation of withdrawal symptoms, based on observation and subject self-report, will be evaluated during Visit 1 (ED, inpatient unit or Clinic) after SUBOXONE and SUBLOCADE. If participants experience precipitated withdrawal, they will be treated symptomatically with medication as described in section 8.4 below.

Health Economics and Outcomes Assessments:

Health economics and outcomes assessments include the include Healthcare Resource Utilization questionnaire (HCRU), the Treatment Effectiveness Assessment (TEA), the Medication Satisfaction Questionnaire (MSQ), and Work Productivity and Activity Impairment Questionnaire: Specific Health Problem (WPAI-SHP).

Statistical Methods:**Prospective Analyses for the Primary and Key Secondary Endpoints:**

The primary endpoint, numbers of subjects who have a repeat OD or OD related death will be analysed using a Cox proportional hazards model controlling for route of administration and comorbid substance use disorder compared to a historical control group and to concurrent subjects who decline SUBLOCADE treatment.

[figure not shown]
The secondary endpoint, treatment engagement as measured by attending the outpatient clinic and receiving subsequent buprenorphine treatment at 3 and 6 months will be analysed using a Cox proportional hazards model comparing patients with primarily intravenous vs non-intravenous routes of opioid use.

Planned Analyses:

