3.2 Secondary

The key secondary endpoints of the study are:

- Numbers and percent of patients in buprenorphine treatment at 3 and 6 months after opioid OD comparing patients who have primarily intravenous to non-intravenous opioid use.

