14.8 Handling of Missing Data

In general, missing data (caused by premature discontinuation or otherwise) will not be imputed. However, missing urine drug screen data will be imputed based on previously defined methods in other patient populations. The secondary endpoint is time attending clinic and patients failing to appear will be considered to have stopped attending at the date of last visit after they've missed 5 consecutive visits. Any missing covariates will be handled via appropriate multiple imputation techniques.

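### The key secondary endpoint is a status at two dates in some sections and a duration in others, with a different model for each and no decisive time point

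*Combined protocol and SAP*

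**What the plan says.** **Status at two dates.**
- The synopsis gives the key secondary endpoint as "Treatment engagement as measured by attending the outpatient clinic and receiving subsequent buprenorphine treatment at 3 and 6 months". It lists "Numbers and percent of subjects in treatment at 3 and 6 months after opioid OD" as a further, non-key secondary endpoint.
- Section 3.2 makes nearly the same count the key secondary endpoint: "Numbers and percent of patients in buprenorphine treatment at 3 and 6 months after opioid OD", compared between primarily intravenous and non-intravenous users.
- Section 14.7.2 fits this form: "Treatment retention at 3 and 6 months will be analysed utilizing a logistic regression", for the same comparison. Table 2 repeats it.

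**Duration.**
- Synopsis, Statistical Methods: engagement "will be analysed using a Cox proportional hazards model comparing patients with primarily intravenous vs non-intravenous routes of opioid use".
- Section 14.8: "The secondary endpoint is time attending clinic". A subject is treated as having stopped on the date of the last visit once five consecutive visits have been missed.

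**A neighbouring rule.** Section 6.4.4 treats a subject as having ceased treatment and withdrawn after missing five consecutive weeks' worth of visits.

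Section 14.2 gives a type I error rate and power for the primary endpoint only. No error rate, power or testing order is given for the key secondary endpoint.

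**The concern.** A hazard ratio for stopping, an odds ratio at 3 months and an odds ratio at 6 months are three different quantities, each with its own p-value. The current text supports all three. The study is open-label (Section 9.1.4), so retention by route of use can be seen before a model is chosen, and whichever result is reported could be described as the planned one.

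The two forms can also classify the same person differently. Appendix 2 schedules counselling at all 19 clinic visits from Visit 2 to End of Treatment, but an injection at only six of them (Visits 3, 7, 11, 15, 17 and 19). A subject who keeps attending but no longer receives buprenorphine is still attending clinic under Section 14.8 and is not in buprenorphine treatment under Section 3.2.

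**Working it through.** **No planned figure to reproduce.** The only sample-size figure (80% power, Section 14.2) belongs to the primary endpoint. This point does not rest on it.

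**1. Two forms, two models**

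| Place | Form | Model |
|---|---|---|
| Synopsis, endpoint list | status at 3 and 6 months | – |
| Section 3.2 | status at 3 and 6 months | – |
| Section 14.7.2, Table 2 | retention at 3 and 6 months | logistic |
| Synopsis, Statistical Methods | engagement at 3 and 6 months | Cox |
| Section 14.8 | time attending clinic | – |

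A Cox model needs a duration, which Section 14.8 supplies. A logistic model needs a yes/no status, which Section 3.2 supplies. No sentence ranks the two.

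**2. Illustration of size.** From the documents: about 100 treated subjects (Section 5.1). Assumed, because the documents give nothing: 60:40 intravenous to non-intravenous, exponential stopping times, hazard ratio 1.8 with faster stopping in the intravenous group, 50% retained overall at day 168 (range 30–70%), day 84 as 3 months, two-sided 5% tests.

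If s is 6-month retention in the non-intravenous group, then 0.6·s^1.8 + 0.4·s = 0.5, so s ≈ 0.62 and the intravenous group retains 0.62^1.8 ≈ 0.42. At the halfway date the figures are the square roots: about 0.79 and 0.65.

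Approximate power by hand:
- Logistic, 6 months: log odds ratio = ln(0.62/0.38) − ln(0.42/0.58) = 0.81; SE = √[1/(60·0.42·0.58) + 1/(40·0.62·0.38)] = 0.42; z ≈ 1.94; power = Φ(1.94 − 1.96) ≈ 49%.
- Logistic, 3 months: log odds ratio ≈ 0.69; SE ≈ 0.47; z ≈ 1.46; power ≈ 31%.
- Cox: 50 stops; SE of the log hazard ratio = 1/√(50·0.6·0.4) = 0.29; z = 0.588/0.289 ≈ 2.04; power ≈ 53% (about 49% when simulated).

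Cox and 6-month logistic have similar power; the 3-month test is the weak one. Simulation shows how often the verdicts differ:

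| Pair of tests | Disagree, 50% retained | 30–70% retained |
|---|---|---|
| Cox vs 6-month logistic | about 6% | about 3–11% |
| 3-month vs 6-month logistic | about 31% | about 24–33% |

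**3. False positives with no difference.** Two independent 5% tests would give 1 − 0.95² = 9.75%. The tests here are correlated. At 50% retained, at least one rejects in 5.9% (Cox plus 6-month logistic), 8.0% (3- plus 6-month logistic) and 8.7% (all three).

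**4. Other shapes of effect** (assumed, 50:50 split; intravenous vs non-intravenous retention at 3/6 months):
- Early difference that closes, 45/40% vs 70/45%: power 22% (Cox), 73% (3 months), 9% (6 months). Cox and 6-month logistic disagree in 15%.
- Late difference, 60/30% vs 65/55%: power 58%, 8% and 74%. Cox and 6-month logistic disagree in 17%.

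**5. Stopping rules.** Visits are weekly to day 92, so five visits and five weeks then nearly coincide. After that they separate. A subject last seen on day 106 (Visit 16) has four scheduled visits left (days 120, 134, 148 and 169) and can never miss five. The same subject passes five weeks at about day 106 + 35 = 141. The two sections therefore treat this subject differently just before the 6-month assessment.

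**The case against.** The body of the protocol is more coherent than a list of differences suggests. Sections 3.2 and 14.7.2 and Table 2 fit together as a binary status with a logistic model. The outliers are one synopsis sentence and one sentence in a missing-data section whose job is to date dropout. That stands, and it makes the correction easy, but no rule in the document says the body prevails.

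Three stronger readings are tempting, and the documents do not support them.
- **Three separate definitions.** The synopsis endpoint and Section 3.2 both describe buprenorphine status at 3 and 6 months. The real split is status against duration.
- **The choice between Cox and logistic drives the result.** Under a steady effect, all three tests fail to agree in about 32% of trials, but nearly all of that comes from the 3- and 6-month tests, which both sit inside Section 14.7.2. It would remain after the synopsis was corrected.
- **Table 2 adds another competing Cox test.** Its Cox row for retention compares ED with outpatient initiation and is exploratory. It is a different question.

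It is also fair that this comparison is non-randomised, lies within the treated group, and carries no assigned alpha or power. It cannot support a claim about the treatment's effect, and that limits the severity.

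**Conclusion.** The point holds: the key secondary endpoint appears as a status and as a duration, with logistic regression for one and Cox for the other, and the plan leaves open which governs and which date decides. It should be fixed before the analysis. It does not touch the primary endpoint, and a reader should not infer that it does.

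The sizes are illustrations only. For a steady hazard ratio of 1.8 the model choice changes the significance verdict in about 3–11% of trials and the time point in about 24–33%. With no difference, free choice among the three tests gives about 8–9% false positives. If the retention curves converge or separate late, disagreement between the models can be larger. The wording conflict and the day-106 gap need no such assumptions, because they follow from the text and the visit schedule.

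**What to change.** 1. In the synopsis, replace the Cox sentence with the Section 14.7.2 logistic regression. Keep Cox, if wanted, as a supportive analysis with a confidence interval and no test. Use one key secondary definition in the synopsis and Section 3.2.
2. In Section 14.8, replace time attending clinic with the Section 3.2 status. Classify it by receipt of buprenorphine within a stated visit window for 3 and 6 months, not by attendance alone. The 6-month window needs care: the last scheduled injection is at day 148 and none is scheduled at the day 169 visit.
3. State before the analysis how the two dates are handled: for example, test 6 months first and 3 months only if that is significant, or report 3 months with a confidence interval only. Carry this into Section 14.7.2 and Table 2.
4. Reconcile the missed-visit rule in Section 14.8 with the missed-weeks rule in Section 6.4.4, so that each subject has one classification for analysis.

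The cost is wording in the synopsis, Sections 3.2, 14.7.2 and 14.8, and Table 2, plus the reconciliation with Section 6.4.4. No visit, data item or sample size changes. The small downside is that the 3-month result is no longer an independent 5% test.
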